9.0 Confidentiality, Privacy and Data Management

9.1 Confidentiality

9.1.1 Identifiers associated with data and/or specimens

See HRP-598 Research Data Plan Review Form

9.1.1.1 Use of Codes, Master List

See HRP-598 Research Data Plan Review Form

9.1.2 Storage of Data and/or Specimens

See HRP-598 Research Data Plan Review Form

9.1.3 Access to Data and/or Specimens

See HRP-598 Research Data Plan Review Form

9.1.4 Transferring Data and/or Specimens

See HRP-598 Research Data Plan Review Form

9.2 Subject Privacy

See HRP-598 Research Data Plan Review Form

10.0 Data and Safety Monitoring Plan

10.1 Periodic evaluation of data

Adverse event reporting will be reviewed at regular research meetings led by principle investigator. Annual reports will be made to the Penn State IRB as per the current protocol.

10.2 Data that are reviewed

Adverse events are defined as unfavorable medical changes that occur during or after the study initiation, that may or may not be related to or caused by study participation. Adverse events are not procedures or surgeries (the medical condition that caused the need for the procedure or surgery is the adverse event or pre-existing conditions or illnesses that do not worsen during the study period. The intensity of the event will be evaluated and recorded as one of the following:

Mild intensity – events may or may not be volunteered by the patient. The patient is aware of the event but it is easily tolerated.

Moderate intensity – signifies discomfort sufficient to interfere with normal activities. A change in therapy may or may not be indicated.

Severe intensity – side effects are almost always brought up by the patient, definitely interfere with functioning, and require a medical intervention.

The investigator will be obligated to pursue and provide information as requested by the FDA, when applicable. In general, this will require a description of the event in sufficient detail to allow for a complete medical assessment of the case and independent determination of possible causality. Information on other possible causes of the event, including concomitant medications and illnesses, must be provided. The investigator's assessment of causality must also be provided. If causality is unknown, it should be attributed to study participation. The certainty of the relationship of the event to

study participation will be recorded as "Possible Related" or Not Possibly Related." The situation surrounding the event should be assessed to determine whether it is related to the study.

10.3 Method of collection of safety information

Study data will be managed using REDCap (Research Electronic Data Capture), a secure web application designed to support data capture for research studies, providing user-friendly web-based case report forms, real-time data entry validation (e.g., for data types and range checks), audit trails, a randomization module, and a de-identified data export mechanism to common statistical packages (SPSS, SAS, Stata, R/S-Plus).

Well-designed data collection forms (i.e. CRFs) will be developed to minimize data collection and recording errors. Separate data collection forms will be designed based on who is collecting the data and when and where the data are collected. Forms will be designed to collect cumulative information such as adverse events and the use of concomitant medications.

10.4 Frequency of data collection

All data collection will begin immediately upon enrollment.

10.5 Individuals reviewing the data

The PI will receive immediate notification of all serious adverse events, and a regular report summarizing recruitment and all other adverse events. The required offices will be notified immediately of SAEs as per our safety plan and a summary of the reported adverse events will be presented per policy.

10.6 Frequency of review of cumulative data

Refer to section 10.5

10.7 Statistical tests

Refer to section 10.2

10.8 Suspension of research

Not applicable

11.0 Risks

Risks of Norethindrone: Serious adverse reactions with the use of norethindrone are serious cardiovascular events and stroke, vascular events, and liver disease. Adverse reactions commonly reported by norethindrone users are: Irregular uterine bleeding, nausea, breast tenderness, and headache

Risks of Low Dose naltrexone: Adverse reactions to low dose naltrexone can include hepatotoxicity, depression and suicidality, allergic reactions, eosinophilic pneumonia, muscle cramps, dizziness or syncope, somnolence or sedation, decreased appetite, and insomnia. Everyone taking part in the study will be watched carefully for side effects; however, doctors do not know all the discomforts and risks that may happen. With all drugs there is the possibility of complications and side effects that are not known at this time. These may be mild or serious, and in some cases may be very serious, long-lasting, or may never go away. There is also a risk of death.

If you experience any side effect (or other health issues) during this study, let your study doctor know immediately. If you are not honest about your side effects, you may harm yourself by staying in this study. If you do not understand what any of these side effects mean, please ask the study doctor or study staff to explain the words to you.

Common side effects of naltrexone at higher doses include:

- Nausea, vomiting, diarrhea or constipation
- Stomach pain or cramping
- Loss of appetite
- Headache
- Dizziness
- Nervousness, irritability, or anxiety
- Tearfulness
- Increased or decreased energy

This study plans on using low dose naltrexone at a much lower dose than typically available. Multiple studies have used similar doses of naltrexone (3 - 4.5 mg) in both adult and children with no significant adverse reactions. There is no evidence reported of interactions of low dose naltrexone with other medications. The most commonly reported side effects in studies using low dose naltrexone include:

- Difficulty falling and/or staying asleep (insomnia)
- Vivid dreams
- Headaches.

Though it is an uncommon event, there is a risk of unexpected allergic reaction to the study drug which may include hives, rash, swelling or difficulty breathing. If one of the mentioned symptoms appears, stop taking your study drug(s) and seek immediate medical help.

Risk of Loss of Confidentiality: There is a slight risk of loss of confidentiality associated with participation in the study. To mitigate this risk, all subjects will be assigned a unique study ID that will be used throughout the study to identify each subject. The list linking identifiable information from the study ID will be maintained in the REDCap database designed for this study. REDCap uses secure passwords and access to the database would be restricted to study personnel.

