2.3 Study Rationale

Naltrexone hydrochloride is a well-known, competitive opioid antagonist traditionally used to treat opioid overdose or addiction. At much lower doses, naltrexone has significantly different pharmacologic properties. Low-dose naltrexone (LDN) acts on non-opioid receptors in the central nervous system to decrease activation of microglial cells and decrease plasma levels of multiple inflammatory cytokines. LDN has also been shown to transiently block all three subtypes of opioid receptors (μ , κ , δ) resulting in an upregulation of not only opioid receptors, but also increasing endogenous opioid production. Early studies of LND in other inflammatory disorders, such as inflammatory bowel disease and fibromyalgia, have demonstrated promising results. Since the pelvic pain associated with endometriosis is due in part

to increased peritoneal inflammation, LND has the potential to provide non-narcotic analgesic relief by decreasing endometriosis-associated inflammation.

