3.0 Inclusion and Exclusion Criteria

3.1 Inclusion Criteria

Inclusion

- Premenopausal female ages 18 to 45 years old on the day of signing informed consent.
- Must agree to use only study-specific analgesic medications during the study and is not known to be intolerant to them.
- Diagnosed with endometriosis and has had, within the last 10 years prior to signing the informed consent, surgical diagnosis with direct visualization and/or histopathologic confirmation of endometriosis.
- Is not expected to undergo gynecological surgery or other surgical procedures for treatment of endometriosis during the study period.
- Agrees to use contraception if not surgically sterile during the entire study.
- Patients using oral contraceptives, LARCs and/or GnRH agonists/antagonists for contraception and/or management of endometriosis, with a stable regimen, will be able to continue in the study, however, women using oral contraceptives and GnRH agonist/antagonists will be switched to Norethindrone acetate during the 1-2 week run-in period as prescribed by principle investigator.

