3.2 Exclusion Criteria

Exclusion

- Women that are pregnant, breastfeeding or trying to conceive.
- Patients with chronic daily opioid use and any chronic pain or frequently reoccurring pain condition, other than endometriosis, that is treated with opioids or requires analgesics for more than 7 days per month.
- Patients with abnormal liver function tests (greater than 3x normal limit) in the past year or history of liver disease. Routine screening of liver function is not required.
- Non-English speaking or inability to read and understand English secondary, in part, to the need to read and report daily results in English.
- Undiagnosed vaginal bleeding
- Patients with history of opioid, illicit drug or alcohol abuse
- Patients currently taking thioridazine
- Patients with a history of suicidality
- Patients with current or history of unstable depression or other psychiatric disorder who, by PI judgement, are unstable or not well controlled
- Known, suspected or history of cancer of the breast
- Active deep vein thrombosis, pulmonary embolism or history of these conditions
- Active or recent arterial thromboembolic disease (e.g., stroke, myocardial infarction)

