4.4 Eligibility/screening of subjects

When the study team receives information about a potential subject, follow-up is made to verify eligibility. If excluded, no further questions are asked and they are thanked for their time. If eligible the subject is scheduled for a visit.

Follow-up includes a phone screen of the potential subject by asking questions such as, ensuring the subject is premenopausal and in between the ages of 18 and 45 years old, agree to only use study-specific analgesic medications during the study and if intolerance to oxycodone and ibuprofen are known, agrees to use Norethindrone acetate and either their LARC or other barrier contraception while in the study, if the subject plans on becoming pregnant or trying to conceive at any point during the study, if the subject has any chronic daily narcotic use and any chronic pain other than endometriosis, and verify the subject is able to speak and read English to answer the surveys. We will also confirm that the subject is willing and able to be reliably contacted by email for study specific purposes.

If the participant passes the phone screen, the participant will be scheduled for a screening visit. After consent and receiving Norethindrone acetate, an email will be sent for the subject to complete the daily surveys for next 6-7 days. Upon completion of the surveys, the participant will pass or fail the screening process.

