Study subjects will receive education on analgesics approved for use in the study which are also within the standard of care for the management of pelvic pain associated with endometriosis. As standard of care for these patients, study subjects will be instructed to take ibuprofen as first time treatment and acetaminophen if additional pain relief is needed, both of which are available over the counter. Only if requested will a stronger medication be prescribed like oxycodone. If needed, to relieve pain, the subject will be advised to take first the ibuprofen 600 mg every 6 hours as needed for pain with food, then acetaminophen 1000mg every 6 hours as needed for pain. Subjects needing additional pain relief will need to discuss this with the study team in which oxycodone 5 mg every 6 hours as needed for pain will be prescribed. Refill prescriptions for opioid pain medication will be provided using the same dose and quantity beyond the screening visit on an as needed basis and will not be routinely provided at any subsequent study visits unless there is a documented need. The subject will complete an EPH-30 and PGAs surveys at the visit. The subject will be instructed to complete their daily surveys which include the VAS and medication compliance. We will also review and record any adverse events. At this time, we will also review compliance of daily reporting since the previous visit. Surveys will be sent via email through a secure link with RedCap and completed on-site during the visit.

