8.3 Statistical methods

The VAS scores will be collected daily from 1-week pre-intervention to 12 weeks postintervention. Prior to analysis, the AUC VAS scores will be calculated per participant separately for the 1-week pre-intervention period and the randomization to 12 weeks post-intervention period. Subsequently, the AUC VAS score data will be normalized per participant to an average AUC VAS score per week (i.e., 7 days) to account for participants that withdraw early from the study. The primary outcome of interest is the AUC VAS scores from randomization to 12 weeks post-intervention period. For this primary outcome, a linear mixed-model will be used to compare the average AUC VAS scores from randomization to 12 weeks post-intervention between the two intervention groups, adjusting for the covariate of opioid intake during the 12-week trial as measured in morphine equivalent units (MEUs)) and using the subject as a random effect in the model.

A secondary analysis with AUC VAS scores as the outcome will use a linear mixed-effects model having intervention group, the repeated factor of time period (1-week pre-intervention and randomization to 12 weeks post-intervention), the interaction of intervention group and time period, and the covariate of opioid intake during the trial as fixed effects and the participant as a random effect. Contrasts will be constructed from this mixed model to compare within and between the intervention groups with respect to AUC VAS scores. Similarly, linear mixed-effects models will be used to compare the two interventions over time with respect to the outcomes of PGIC and EHP30 which are collected at 4-week intervals over the course of the trial. Another secondary analysis will fit a linear random coefficients model to the weekly VAS scores (i.e., not AUC) to generate linear trajectories for each intervention group, adjusting for the covariate of opioid intake. From these trajectories, estimates for the rate of change (i.e., slope) over time in VAS scores will be compared between the two intervention groups. In the event linear trajectories do not fit the data well, higher order polynomials (e.g., quadratic) will be considered to estimate the curve trajectory per intervention.

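### Section 11 reports no interactions for low dose naltrexone without excepting opioids, and no step before the first dose acts on recent opioid intake

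*Combined protocol and SAP*

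**What the plan says.** **The interaction statement.** Section 11.0 contains one sentence on interactions: "There is no evidence reported of interactions of low dose naltrexone with other medications". Nothing else in that section qualifies it for opioids.

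**The pharmacology.** Section 2.3 says "LDN has also been shown to transiently block all three subtypes of opioid receptors". Section 2.1 adds that about a tenth of the usual dose has different effects. It also reports a hypothesis of brief, incomplete receptor blockade followed by greater opioid production and sensitivity.

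**Opioids in the trial.** After ibuprofen and acetaminophen, a subject who asks for more relief discusses it with the study team, and "oxycodone 5 mg every 6 hours as needed for pain will be prescribed" (Section 7.2.2). Section 8.3 specifies the primary model as "adjusting for the covariate of opioid intake during the 12-week trial as measured in morphine equivalent units". Section 7.4.6.5 prohibits no medication.

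**Eligibility.** Section 3.1 requires that a subject "Must agree to use only study-specific analgesic medications during the study and is not known to be intolerant to them". Section 3.2 excludes "Patients with chronic daily opioid use and any chronic pain or frequently reoccurring pain condition, other than endometriosis, that is treated with opioids", and separately a history of opioid abuse. The phone screen in Section 4.4 asks "if the subject has any chronic daily narcotic use and any chronic pain other than endometriosis".

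**Before the first dose.** Section 7.2.1 notes that narcotic use is assessed in routine clinic visits. The visit table in Section 7.1 has analgesic use reported daily in the run-in. Section 7.2.2 has staff review completion of those reports at Visit 1, where the first dose is taken in front of study personnel.

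**The concern.** The study drug acts on the receptors that the permitted rescue drug uses. The risk section, which addresses subjects directly in places, tells its reader that no interactions are reported and stops there. A subject or clinician relying on that section has no specific prompt to think about oxycodone.

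The procedures have the matching gap. Staff collect information on opioid use before the first dose, but no rule says what to do with it. Intermittent opioid use for endometriosis pain is not excluded, so a woman can reach Visit 1 having taken an opioid hours earlier and receive naltrexone on the spot. What is at stake is patient safety at and after the first dose.

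**Working it through.** The main check is a comparison of provisions. Each one that touches opioids before the first dose is tested on one question: does it act on recent or intermittent intake?

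| Provision | What it covers | Acts on recent intake before first dose? |
|---|---|---|
| Analgesic restriction (3.1) | Limits subjects to study analgesics | No; oxycodone is one of them (4.4, 7.2.2) |
| Chronic daily use exclusion (3.2) | A long-term pattern of use, joined by *and* to a pain condition other than endometriosis | No |
| Opioid abuse exclusion (3.2) | History of abuse | No |
| Phone question (4.4) | Chronic daily use | No |
| Routine narcotic assessment (7.2.1) | Use known to the clinic | No action attached |
| Monthly prescription verification (1.3) | Prescriptions, as a secondary outcome | No action attached |
| Daily run-in reports (visit table, 7.1) | Analgesic use by day | Recorded; no action attached |
| Run-in threshold (7.1, 7.2.1) | At least 6 of 7 entries | No; it counts entries, not their content |
| Visit 1 review (7.2.2) | Completion of daily reporting | No rule on opioid content |
| Supervised first dose (7.2.2) | Staff present at dosing | No opioid question, no deferral rule |

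Every row falls short in the same way: there is no look-back question, no opioid-free interval and no rule for delaying the dose.

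Three small calculations bear on the fix.

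1. **Why the run-in reports alone are not enough.** A subject passes with 6 of 7 entries, so 7 − 6 = 1 day can be missing, and 1/7 = 14% of the week. The missing day may be the last one. A direct question at Visit 1 is needed as well.

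2. **Norethindrone cover during a deferral.** Section 7.2.1 dispenses a 2-week supply, or 14 days. After one run-in week 14 − 7 = 7 days remain; after two, 14 − 14 = 0. Section 7.4.2 caps norethindrone at 14 weeks. Two run-in weeks plus 12 treatment weeks already make 14, so any deferral after a second run-in week exceeds the cap by its own length.

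3. **Sample size.** The plan's figure reproduces. For a standardized difference of 0.5 at two-sided 0.05 and 80% power, a t-test needs 63.77, so 64 per arm. Then 64 / 0.8 = 80 per arm, or 160 in total. A short deferral before randomization does not change this.

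**The case against.** The strongest case on the other side is that no error has been shown. The sentence in Section 11 may be an accurate account of reported low-dose evidence. A reader might infer that it is false, or that the study drug will block oxycodone or cause harm after an opioid. The documents do not support either reading. Section 2.1 says the low dose behaves differently, and its hypothesis contains both a blockade phase and a phase of increased sensitivity, so even the direction of any effect on oxycodone is open. This stands, and it limits the point to an unqualified statement and a missing check.

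A reader might also infer that subjects go unwarned. That cannot be said. Section 5.1 has the whole consent form reviewed with each subject, and its text was not available.

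The safeguards are real. Oxycodone comes only on request and after discussion with the study team, so for study prescriptions the prescribers know of it. It would be wrong to say that staff ignore the run-in reports, since they review whether these were completed. But knowing of a prescription is not the same as knowing when the last tablet was taken.

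The refill sentence, "Refill prescriptions for opioid pain medication will be provided using the same dose and quantity beyond the screening visit on an as needed basis", could be read as proof that opioids are prescribed at screening, about a week before the first dose. It suggests this but does not state it, and the screening steps in Section 7.2.1 list no opioid prescription. The point does not depend on it.

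Finally, frequency is unknown. The 56.3% in Section 2.2 is the share filling at least one narcotic prescription over two years. It cannot be turned into a rate of use shortly before Visit 1.

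**Conclusion.** The point holds in a limited form. Section 11 makes no exception for opioids in its only interaction statement, although the protocol's own pharmacology and its own rescue plan make one relevant. Under the procedures as written, recent opioid intake neither prompts a question nor delays the first dose.

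No number of affected women can be given, because the documents supply no rate. They do not establish the size or direction of any effect either. The conclusion rests on the receptor action stated in Section 2.3, on oxycodone being permitted, and on the absence of any rule linking the two before dosing. It makes no claim about the consent form. This is a cheap improvement to patient safety. It leaves the sample size and the planned analysis as they are.

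**What to change.** 1. **Section 11.0.** After the interaction sentence, add wording such as: *However, naltrexone acts on opioid receptors. The study drug may change how oxycodone or other opioids work for you, including one taken shortly before your first dose. If oxycodone does not relieve your pain, contact the study team; do not take extra doses.* Use the same wording in both arms, and align the consent form if it lacks this.

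2. **Section 7.2.2, before randomization.** Ask about last opioid use (drug, dose, date and time) and check the answer against the run-in analgesic reports. If it falls within an interval set in advance by the investigator and the investigational pharmacy, defer randomization and first dose together, so that no delay arises after assignment. Keep the qualifying run-in week as the baseline week for the pain score analysis.

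3. **Norethindrone.** Resupply where needed, for example by the shipping arrangement that Section 7.1 already describes for dose adjustments. Extend the 14-week limit in Section 7.4.2 by the length of the deferral for anyone who used both run-in weeks.

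The cost is a short amendment, one added field at Visit 1, occasional short deferrals and some norethindrone resupply. The baseline week may sit slightly further from randomization for deferred women, but the deferral is decided before assignment and so cannot depend on arm.
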